5.4.1.1 General derivation details for relapses

A relapse (confirmed or unconfirmed) is identified from the ‘Relapse Summary’ eCRF with ‘Did the subject experience a relapse’ ticked as ‘Yes’. For each relapse the corresponding start and end date/time, as well as outcome, treatment with corticosteroids, action taken with study drug and need for hospitalization, and whether an EDSS was completed are recorded. For relapses with completed EDSS it is collected whether it qualifies as a confirmed relapse (see definition details for primary efficacy variable above). A relapse which is not a confirmed relapse is considered an ‘unconfirmed relapse’.

Relapses ‘from date of randomization up to EOS date’ include all relapses unless starting prior to randomization. Additional flags will be added for relapses from date of randomization up to EOT + 7 days (relapse start date in respective period), relapses after EOT + 7 days (start date from EOT + 8 days).

Note: Relapses with missing start date are considered to have started on randomization date for analysis. Relapses with partial start date are considered to have started at the lower limit (but earliest on randomization date).

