5.4 Efficacy variables

5.4.1 Primary efficacy variable(s): ARR up to EOS

The primary endpoint is the Annualized Relapse Rate (ARR) up to EOS, based on confirmed relapses according to the treating neurologist / principal investigator. ARR is defined as the number of confirmed relapses per subject-year.

For subjects completing the study as planned the EOS is scheduled to occur at least 108 weeks (± 7 days) after randomization.

More precisely, for subjects prematurely discontinuing treatment the EOS is scheduled to occur 108 weeks (± 7 days) after randomization. For subjects completing the 108-week treatment period the EOS is scheduled to occur prior to entry into the open-label extension (14–22 days after EOT, or 23–37 days after EOT in exceptional cases) or after the safety follow-up period for subjects not entering the open-label extension (30–37 days after EOT).

A confirmed relapse is defined as a record with ‘Relapse meeting the criteria for a confirmed relapse?’ answered ‘Yes’ on the ‘Relapse Summary’ eCRF. All confirmed relapses from randomization up to EOS will be included in the analysis.

For the statistical analysis of ARR, the following data will be used:

- Number of confirmed relapses from date of randomization up to EOS date;
- Length of observation expressed in years, defined as: $[\text{EOS date} - \text{date of randomization} + 1]$ in days, divided by 365.25.

The logarithm of the length of observation up to EOS will be used as an offset variable in the primary efficacy and sensitivity analyses.

Confirmed relapses ‘from date of randomization up to EOS date’ includes all confirmed relapses unless starting prior to randomization.

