12 HANDLING OF MISSING/INCOMPLETE DATE AND TIME FIELDS

In the following, ‘lower limit’ and ‘upper limit’ refer to the minimum or maximum, respectively, of a possible date. For example, if the day is missing, the lowest limit is the first day of the given month and the upper limit is the last day of the given month. If the day and month are missing, the lower limit refers to the first day of the given year and the upper limit to the last day of the given year. *The earliest and the latest dates refer to the first or last date, respectively, when ordered in sequence.*

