12.2 Relapse

Type of date/time	Date/time is incomplete	Date/time is missing
Relapse start date (collected on ‘Relapse Summary’ eCRF)	Maximum of lower limit and randomization date Unless upper limit is prior to randomization date, then upper limit	Randomization date

eCRF = electronic case report form.

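### SAP 5.4.1.1 and the 5.4.1.2.8 note omit the exception in 12.2 for partial relapse dates wholly before randomization, so such a relapse is counted under one rule and excluded under the other (minor)

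*SAP*

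**What the plan says.** Four places in the SAP bear on this.

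- **Section 5.4.1** (primary variable). The count of confirmed relapses from randomization to end of study "includes all confirmed relapses unless starting prior to randomization". Section 5.4.1.1 applies the same condition to relapses in general: they "include all relapses unless starting prior to randomization".
- **Section 5.4.1.1** (general relapse derivations), in its closing note: "Relapses with partial start date are considered to have started at the lower limit (but earliest on randomization date". The note to Section 5.4.1.2.8 (ARR by period) repeats this for assigning relapses to periods. Neither note has an exception.
- **Section 12.2** (incomplete relapse start dates on the Relapse Summary eCRF). The imputed date is "Maximum of lower limit and randomization date", followed by the exception "Unless upper limit is prior to randomization date, then upper limit".
- **Section 12** (introduction). Lower and upper limits are the earliest and latest dates that the partial date allows.

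A completely missing start date is set to the randomization date in all three places, so there is no conflict there.

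**The concern.** The imputed start date decides whether a relapse enters the primary count. Followed literally, the 5.4.1.1 note can never return a date before randomization. A relapse known from its month or year to have begun earlier is therefore moved to the randomization date and passes the inclusion test in 5.4.1. That defeats the test for the very records it should remove. Section 12.2 handles the same record correctly.

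Neither section refers to the other for this rule, and neither claims precedence. A programmer working from 5.4.1.1 and an independent programmer working from Section 12 could each follow the SAP and derive different counts for the same subject. The affected variables are those built on these start dates: ARR up to end of study, ARR up to end of treatment plus 7 days, ARR for all relapses, the first period in the ARR-by-period analyses, and time to first confirmed relapse (5.4.4.1).

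**Working it through.** **Inputs.** Let L and U be the earliest and latest possible dates of a partial onset date (Section 12), and R the randomization date.

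- Rule A (5.4.1.1 and the 5.4.1.2.8 note): start = max(L, R).
- Rule B (12.2): start = U if U < R; otherwise start = max(L, R).
- Inclusion (5.4.1 and 5.4.1.1): count the relapse if start ≥ R.

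**Comparison.** Assume R = 10 May 2016, for illustration only.

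| Recorded onset | L | U | Rule A | Counted? | Rule B | Counted? |
|---|---|---|---|---|---|---|
| April 2016 | 1 Apr 2016 | 30 Apr 2016 | 10 May 2016 | yes | 30 Apr 2016 | no |
| 2015 | 1 Jan 2015 | 31 Dec 2015 | 10 May 2016 | yes | 31 Dec 2015 | no |
| May 2016 | 1 May 2016 | 31 May 2016 | 10 May 2016 | yes | 10 May 2016 | yes |
| 2016 | 1 Jan 2016 | 31 Dec 2016 | 10 May 2016 | yes | 10 May 2016 | yes |
| June 2016 | 1 Jun 2016 | 30 Jun 2016 | 1 Jun 2016 | yes | 1 Jun 2016 | yes |

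The rules disagree only in the first two rows, where U < R. There the relapse certainly began before randomization, yet Rule A counts it on Day 1. For every other partial date they agree.

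**Size of one wrongly counted relapse.** The SAP gives no figure to reproduce, so this is an illustration. It assumes the 1133 randomized subjects split evenly (1133 / 2 ≈ 566 per arm) and are all followed to Week 108.

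- Follow-up per subject: 108 × 7 / 365.25 = 756 / 365.25 ≈ 2.07 years.
- Subject-years per arm: 566 × 2.07 ≈ 1,172.
- Effect on an arm's raw ARR: 1 / 1,172 ≈ 0.0009.
- Effect on the raw ARR for the first 12-week period (Days 1–84): 566 × 84 / 365.25 ≈ 130 subject-years, and 1 / 130 ≈ 0.008.

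With shorter real follow-up the denominators shrink and the effect per record rises in proportion.

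**After the fix.** With the 12.2 exception in both notes, all three places give the Rule B columns. The first two rows change from counted to not counted, and nothing else moves.

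**The case against.** The strongest defence is that the SAP already gives the right answer. Section 5.4.1 excludes relapses starting before randomization, and 5.4.1.1 repeats this ahead of its note. A relapse dated April 2016 in a subject randomized on 10 May is known to be earlier and could be dropped without imputing a date. Section 12 is the dedicated section for incomplete dates, and the notes can be read as a short form of 12.2. That is probably the intent. But the notes do not say that exclusion comes before imputation, and no section says that 12.2 prevails, so the contradiction stands.

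A second defence is that there may be no such records, and this largely stands. An affected record must be on the Relapse Summary eCRF, have a partial onset date and lie wholly before randomization. For the primary analysis it must also be confirmed, which requires a completed EDSS. Relapses from the subject's history go on a separate form (Section 5.2.2). The visit schedule marks a relapse assessment at Baseline, and deviation PD_PP.020 covers relapses shortly before or after the baseline EDSS. Neither shows that such a relapse would be entered as an on-study relapse.

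A reader might infer that every analysis using relapse dates is affected. The SAP does not support that. The 12-week and 24-week confirmed disability accumulation derivations use relapse dates only to rule out EDSS confirmation during a relapse, and they follow a separate partial-date rule in 5.4.2.3.1. Nor does Section 5.4.1, which defines the primary variable, itself contain the faulty rule. That rule is in the derivation notes of 5.4.1.1 and 5.4.1.2.8.

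**Conclusion.** The contradiction is certain, and its likely effect is very small. Read literally, 5.4.1.1 and the 5.4.1.2.8 note give a result contrary to the inclusion rule in 5.4.1, while 12.2 agrees with it. This is a wrongly stated rule in the derivation of the primary variable, not just a missing detail.

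One affected record adds about 0.0009 to an arm's raw ARR over the whole study, or about 0.008 to the first 12-week period, under the assumptions of an even split and full follow-up. The number of affected records is not stated and may be zero. It would be tempting to conclude that the primary result is biased, but the SAP does not support this. Such relapses would precede treatment in a randomized, double-blind study, so there is no reason to expect more of them in one arm, and a handful could hardly change a conclusion. The severity is minor.

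**What to change.** Make the same change in 5.4.1.1 and in the note to 5.4.1.2.8, in one of two ways:

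- add the exception that, when the upper limit of a partial start date is before randomization, the upper limit is used and the relapse is not counted; or
- delete the partial-date sentence and refer to Section 12.2.

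The cross-reference is safer, because the rule then stands in one place. The rule for completely missing dates and the separate rule in 5.4.2.3.1 need no change. The cost is two lines of SAP wording and a check that the relapse dataset program follows 12.2. No new data or analysis is needed.

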5.4.1.2 Variables for supplementary analyses of primary endpoint

According to the protocol, several supportive/sensitivity analyses are planned for the primary efficacy endpoint, including the ARR analysis from randomization up to EOT + 7 days, with EOT date defined as date of last drug intake [see Section 11.1]. Those and other additional variables are defined below. Analyses that do not require additional variable derivations will not be mentioned in this section but will be described in the ‘Statistical Analysis’ section, e.g., the ARR up to EOS analysis with treatment as the only covariate uses the same variable as the primary efficacy analysis.

5.4.1.2.1 ARR up to EOT+7 days for confirmed relapses

The variable considers confirmed relapses up to EOT + 7:

- The subject’s number of confirmed relapses from date of randomization up to date of EOT + 7 days;
- Length of observation up to EOT + 7 expressed in years, defined as: [Min (EOT date + 7 days, EOS date) – date of randomization + 1] in days, divided by 365.25.

5.4.1.2.2 ARR up to EOS for all relapses

The variable considers all relapses (confirmed and unconfirmed) up to EOS:

- The subject’s number of all relapses from date of randomization up to date of EOS;
- Length of observation expressed in years, defined as: [EOS date – date of randomization + 1] in days, divided by 365.25.

5.4.1.2.3 ARR up to EOT+7 days for all relapses

The variable considers all relapses up to EOT + 7:

- The subject’s number of all relapses from date of randomization up to date of EOT + 7 days
- Length of observation up to EOT + 7 days, see above.

5.4.1.2.4 ARR up to EOS or per protocol exclusion for confirmed relapses

ARR up to EOS for the per protocol analysis is derived in the same way as the variable for the main analysis but including only confirmed relapses prior to first occurrence of a deviation leading to exclusion from per protocol [see Section 7.1.3]. The considered observation time is derived as for the main analysis but replacing EOS date with the per protocol exclusion date, if available.

Similar variables are derived for ARR up to EOT + 7 days for the per protocol analysis.

5.4.1.2.5 ARR up to the start of alternative DMTs for MS

This variable considers confirmed relapses up to the point where an alternative disease modifying treatments (DMT) for MS is started as follows:

- The subject's number of confirmed relapses from date of randomization up to the day before the start of new DMT for MS or up to EOS date for subjects not starting a new DMT;
- Length of observation expressed in years, defined as: $[\text{Min}(\text{Day before start date of new DMT for MS, date of EOS}) - \text{date of randomization} + 1]$ in days, divided by 365.25.

Start of alternative DMTs for MS is defined in Section 5.2.5.4 and based on study concomitant MS specific therapies. Variables will be derived separately for confirmed and all relapses.

5.4.1.2.6 *ARR up to EOS for imputed confirmed relapses*

Defined in the same way as number of confirmed relapses for the primary analysis unless the confirmation status is missing (e.g., due to the EDSS not being completed). Relapses with missing confirmation status are imputed as confirmed relapses. The length of observation is defined as for the primary analysis.

5.4.1.2.7 *ARR post EOT + 7 days following premature treatment discontinuation*

Defined for subjects prematurely discontinuing treatment with EOS date after EOT + 7 days:

- The subject's number of confirmed relapses from EOT + 8 days to EOS;
- Length of observation expressed in years, defined as: $[(\text{EOS date} - \text{EOT date} + 8) + 1]$ in days, divided by 365.25.

5.4.1.2.8 *ARR by period*

ARR is derived per period. Variables are defined separately for confirmed relapses and for all relapses. The following periods are considered:

ARR up to Week 60

Derived in the same way as for the ARR up to EOS but including only confirmed/all relapses with onset date from randomization date up to Day 420. Observation time is the time from randomization until earliest of Day 420 or EOS.

ARR after Week 60

Derived in the same way as for the ARR up to EOS but excluding confirmed/all relapses with onset date prior to or on Day 420.

ARR by 12-week periods

Similarly, ARR for approximately 3-month intervals are defined: Baseline to Week 12 (Day 1–84), Week 13 to Week 24 (Day 85–168), Week 25 to Week 36 (Day 169–252), Week 37 to Week 48 (Day 253–336), Week 49 to Week 60 (Day 337–420), Week 61 to

Week 72 (Day 421–504), Week 73 to Week 84 (Day 505–588), Week 85 to Week 96 (Day 589–672), after Week 96 (\geq Day 673).

Note: Relapses with missing start date are considered to have started on randomization date for period assignment. Relapses with partial start date are considered to have started at the lower limit (but earliest on randomization date).

5.4.1.2.9 *Number of new or worsening neurological symptoms up to EOS*

The variable is defined as the number of new or worsening neurological symptoms reported on the relapse assessment questionnaire ('Is/was the subject having new neurological symptom(s) or an acute worsening of pre-existing neurological symptom(s)?' answered with 'Yes') from randomization up to EOS.

Each new or worsening neurological symptom is further sub-classified into the following categories: confirmed relapse, unconfirmed relapse, and symptoms not considered a relapse.

Derivation details

Information is taken from the relapse assessment questionnaire eCRF pages ('Phone interview', or 'Relapse Assessment Questionnaire' either 'Visit Interview' or 'Unscheduled Visit Interview'), which have been introduced with protocol version 4.

A new or worsening neurological symptom is linked to a relapse via the onset date ('Date of start of symptoms' corresponding to the new or worsening neurological symptom is identical to the relapse onset date of a relapse reported on the Relapse Summary eCRF). If a symptom cannot be linked to a relapse it is classified as 'Symptoms not considered a relapse'. Symptoms linked to a relapse are further categorized into confirmed and unconfirmed relapses, as per Section 5.4.1.1.

Note that for subjects randomized under protocol versions 1–3 neurological symptoms are only expected to be recorded from the start date of protocol version 4 onwards.

5.4.1.2.10 *Variables for further analyses related to relapses*

Duration of relapse (days) is derived as relapse end date – relapse start date + 1 days.

Relapse symptoms linked to a relapse. The following categories of symptoms are considered: Visual (optic) functions, Brainstem functions, Pyramidal functions, Cerebellar functions, Sensory functions, Bowel and Bladder functions, Cerebral functions, Ambulation, Other relapse symptom taken from the relapse symptoms eCRF.

The **number of functional systems affected** (number of categories, see above) per relapse is derived.

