9.6.5 Supplementary analyses

Supplementary analyses are conducted for other quantities of interest.

9.6.5.1 *ARR up to EOT + 7 days for confirmed relapses*

The primary efficacy model will be repeated only including confirmed relapses up to EOT + 7 days as a response variable, treatment as a factor, the stratification variables and the number of relapses in the year prior to study entry (≤ 1 [or missing] and ≥ 2) as covariates based on the FAS. The model is offset by the log of number of days from randomization up to EOT + 7 days.

The following sensitivity analyses related to confirmed relapses up to EOT + 7 days are conducted:

- *ARR based on confirmed relapses up to EOT + 7 days on the FAS – unadjusted analysis:*

Same analysis as for the main analysis, but with number of confirmed relapses up to EOT + 7 days as a response variable, and treatment as the only factor in the model, i.e., not adjusting for covariates, including stratification variables. The analysis is conducted to assess the effect of adjusting for covariates.

- *ARR based on confirmed relapses up to EOT + 7 days on the FAS – multiple imputation between EOT + 7 days and theoretical Week 108:*

Furthermore, sensitivity analyses based on multiple imputation are conducted based on different assumptions following treatment discontinuation to assess the hypothetical effect if subjects would have stayed on treatment up to Week 108. Multiple imputation methods for count data are applied as for the sensitivity analyses related to the primary analysis [Section 9.6.4.3 and Section 10.1.1]. For subjects who have prematurely discontinued treatment post-treatment events, i.e., the number of relapses between EOT + 7 and theoretical Week 108, will be imputed.

Imputation of events is conducted with the following MI approaches: Missing at Random (MAR), Copy reference, Jump to reference. The corresponding interpretations are detailed in Section 9.6.4.3, only that imputation is now conducted post EOT + 7 days instead of post-study withdrawal.

The resulting rate ratio and corresponding 99% and 95% CIs will be reported and presented in tables and graphically.

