9.6.5.6 ARR post EOT + 7 days following premature treatment discontinuation

This analysis is similar to the analysis described for the primary efficacy variable, using a model with the number of confirmed relapses in the PTO as a response variable, treatment, stratification variables and the number of relapses in the year prior to study (≤ 1 [or missing] and ≥ 2) entry as factors and the logarithm of time between EOT + 8 days and EOS (in years) as an offset variable. The analysis is based on the Post-treatment observation period analysis set (FAS subjects prematurely discontinuing treatment with EOS date after EOT + 7 days).

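### The observation time for the ARR after EOT + 7 days adds 8 days instead of subtracting them, so every subject's denominator is 16 days too long

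*SAP*

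**What the plan says.** Section 5.4.1.2.7 of the SAP sets up a relapse rate for the period after stopping study drug. The population is restricted: "Defined for subjects prematurely discontinuing treatment with EOS date after EOT + 7 days". The numerator is "The subject's number of confirmed relapses from EOT + 8 days to EOS". The denominator is the EOS date minus a term printed as "EOT date} + 8) + 1]$ in days, divided by 365.25", so the whole expression reads [(EOS − EOT + 8) + 1] days, converted to years.

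The analysis of this variable, in section 9.6.5.6, describes its offset differently: "the logarithm of time between EOT + 8 days and EOS (in years) as an offset variable". Section 5.4.1.1 flags the same post-treatment window as "relapses after EOT + 7 days (start date from EOT + 8 days".

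For the companion on-treatment analysis, section 9.6.5.1 says: "The model is offset by the log of number of days from randomization up to EOT + 7 days". Section 5.4.1.2.1 defines that same length of observation in years.

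**The concern.** The numerator and denominator of a rate must cover the same days. Here relapses are counted over a window that starts 8 days after last dose, but the time formula adds 8 days to the interval where it should remove them. A programmer working from the variable definition gets one offset; a programmer working from the analysis section gets another.

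The analysis in 9.6.5.6 is the only planned model confined to relapse activity after drug is stopped. An inflated denominator lowers the reported rate in both arms. Because the excess is a fixed number of days, it weighs most on subjects with short post-treatment follow-up, and it shifts the rate ratio if the arms differ in how long discontinued subjects stay in the study.

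The days offset in 9.6.5.1 is a separate and smaller matter: followed literally, the model-based means would be relapses per day while labelled as annualized.

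**Working it through.** **Inputs**

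- Window: EOT + 8 to EOS, both ends included (5.4.1.2.7; same start day in 5.4.1.1 and 9.6.5.6).
- Day-count convention: end date − start date + 1 (primary endpoint in 5.4.1; time to EOT + 7 in 5.4.1.2.1).
- Eligible subjects: EOS after EOT + 7, so EOS − EOT is at least 8 days.

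**Formula as printed**

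(EOS − EOT + 8) + 1 = EOS − EOT + 9. Dropping the inner bracket changes nothing; the result is still + 9.

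**Formula from the window and convention**

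EOS − (EOT + 8) + 1 = EOS − EOT − 7.

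**Difference**

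(+ 9) − (− 7) = 16 days, or 16 / 365.25 = 0.0438 years, for every subject.

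**Additivity check**

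Time to EOT + 7 plus time after it should equal EOS − randomization + 1. Take a subject with 756 days in total, of which 374 run up to EOT + 7. The remainder is 756 − 374 = 382 days. The printed formula gives 398, and 374 + 398 = 772, which is 16 too many.

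**Effect on a rate, by length of follow-up** (understatement = 16 / days used)

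| EOS at | Correct days | Days as printed | Rate understated by |
|---|---|---|---|
| EOT + 8 | 1 | 17 | 94% |
| EOT + 30 | 23 | 39 | 41% |
| EOT + 37 | 30 | 46 | 35% |
| EOT + 90 | 83 | 99 | 16% |
| EOT + 168 | 161 | 177 | 9% |
| EOT + 365 | 358 | 374 | 4% |
| EOT + 755 | 748 | 764 | 2% |

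**Effect on an arm** (assumed follow-up; the SAP gives none)

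- All subjects stop at Day 378 and reach EOS at Day 756: 371 correct days, 387 as printed; 16 / 387 = 4%.
- Half have 23 correct days and half have 371: mean 197 against 213; 16 / 213 = 7.5%.

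**Effect on the rate ratio** (assumed mean correct follow-up of a days in the ponesimod arm and b in the teriflunomide arm, equal true rates, pooled person-time)

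Apparent ratio = [a / (a + 16)] / [b / (b + 16)].

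| a | b | Apparent ratio (truth 1.00) |
|---|---|---|
| 180 | 180 | 1.00 |
| 240 | 360 | 0.98 |
| 120 | 240 | 0.94 |
| 60 | 300 | 0.83 |

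The arm with the shorter follow-up looks better than it is. Exchanging a and b inverts the ratio.

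**Days against years in 9.6.5.1**

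log(days) = log(years) + log(365.25). The constant is absorbed by the intercept, so the rate ratio and p-value are unchanged, but each arm's model mean is 365.25 times too small to be an annual rate. Section 9.6.5.8 places this analysis in a forest plot that prints the ARR by arm next to the primary ARR.

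**The case against.** The intended definition can be recovered from the SAP itself. The bullet above the formula, section 5.4.1.1 and section 9.6.5.6 all agree on EOT + 8 to EOS, so this looks like one misplaced bracket, possibly even a fault in the copy at hand, and harm arises only if the literal formula is programmed. The variable feeds a single supplementary analysis on a subset defined after randomization. It is outside the multiplicity strategy and is not among the analyses listed for the forest plots, and relapses after discontinuation also enter the primary analysis under the treatment-policy strategy. The large percentages belong to individuals with very short follow-up. Section 5.1.6 schedules EOS for discontinued subjects at Week 108, so person-time should be dominated by longer follow-up. The days wording in 9.6.5.1 would show up at once in the output, and that section says the primary model, which uses years, is repeated.

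Most of this stands as a limit on scope. The primary and secondary results are untouched, and the arm-level effect is probably well below 41%. It does not remove the error. Nothing shows that the bracket was lost in reproduction, and no bracketing of the terms in the order printed short of the correction itself gives the right count. Short follow-up is also possible by design: the PTOP set in 7.1.5.4 admits anyone with EOS after EOT + 7, and 5.1.5 distinguishes those who stay beyond EOT + 30.

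**Conclusion.** The point holds. The formula in 5.4.1.2.7 gives a denominator exactly 16 days too long for every subject, and it contradicts both its own counting window and the offset in 9.6.5.6. If it is programmed as written, the off-treatment ARR is understated in both arms. That direction is certain whenever relapses occur. The size depends on off-treatment follow-up: 4% to 7.5% at arm level in the two assumed cases above, more if short follow-up predominates. Bias in the rate ratio requires unequal follow-up between arms.

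The consequence is confined to the supplementary analysis in 9.6.5.6. The days offset in 9.6.5.1 is a unit inconsistency that spoils the reported ARR by arm but not the treatment comparison.

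**What to change.** - In 5.4.1.2.7, replace the length of observation with [EOS date − (EOT date + 8) + 1] / 365.25.
- In 9.6.5.1, replace the log of the number of days with the log of the length of observation in years from 5.4.1.2.1.
- Check the derivation programs against both. A simple test is that time to EOT + 7 plus time after it equals EOS − randomization + 1 for every subject in the PTOP set.

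The cost is two lines of SAP text and the matching code. No data collection, analysis set or test changes.
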